7.2. Statistical Methods

Primary Analysis: Baseline demographic characteristics of the subjects in the two groups will be examined. If the randomization is executed correctly, we expect no significant difference between the two groups on these variables. If there is an imbalance on certain variables (mostly likely by chance) and these variables also affect the outcomes variables, we will control for these variables using indirect standardization, Mantel-Haenzel stratified analysis or multivariable logistic (for categorical outcome) or linear regression (for continuous outcome). If there is a gross imbalance between the two groups, we will conduct in-depth evaluation to identify factors that may adversely affect randomization. Multivariable logistic and linear regressions will be used to adjust for the imbalance.

We will explore outcomes by clinical site; if there is no significant overall difference among the sites (homogeneous), we will pool sites together. However, if there is significant overall difference, we will identify which site(s) differ from others. Pairwise comparison will be conducted with Scheffe adjustment of significance level. In all following analyses, site will then be an independent variable for adjustment.

Both intent to treat and compliant populations will be analyzed. For categorical data, chi-square test will be used. For continuous variables, t-test will be used if the distribution is normal; otherwise rank-sum test or log transformation will be used. The following outcomes will be evaluated:

- Success rates between study arms for early pregnancy failure;
- Frequency of side effects and serious adverse events between study arms;
- Patient's satisfaction, anxiety, and acceptability of the treatment regimens;
- Cost analysis to compare these two treatments.

The outcome is defined as gestational sac expulsion with one treatment dose on Study Day 3 and no need for surgical intervention or medical intervention within 30 days of treatment. The overall success proportion, along with 95% confidence intervals, will be calculated for each treatment group. The

proportion of successful outcomes within the two treatment groups will initially be compared via calculation of relative risk and odds ratio. The relative strength of the difference in success between groups, as measured by the odds ratio, will be further evaluated via logistic regression. The study population will be summarized overall, and by treatment group, using standard descriptive statistics. Bivariate methods, such as chi-square or Fisher's exact tests (categorical variables) and t-tests or Mann-Whitney U tests (continuous/ordinal variables) will be used to compare the treatment groups' demographic and clinical characteristics. These same methods will be used to initially evaluate differences in the success by demographic and clinical characteristics. The bivariate analyses will be used to select variables for inclusion in subsequent multivariable regression models. We will stratify our results by presenting symptomatology (spotting/cramping etc.). Multivariable logistic regression will be used to evaluate the odds of success within each treatment arm and adjusted for demographics (including race and ethnic variation) and clinical variables that may affect the odds of success. The variables found to be related to the success rate on the bivariate level will be entered one at a time into the model, iteratively comparing the adjusted odds ratios. The final regression models will include the treatment group, study sites, characteristics associated with success rate at the $p < 0.1$ level, as well as covariates that altered the unadjusted ratios by at least 10%. Graphical techniques, such as lowess plots, will be used to assess the assumptions of the models.

The acceptability will be assessed by descriptive statistics. We will query participants using validated instruments [9,11,63] about perceived acceptability of the procedure, adverse effects, pain, bleeding, and duration of symptoms and treatment, as well as whether the procedure met the expectations for the experience, would be chosen again, and would be recommended to a friend. The mean values \pm standard deviation of the VAS measurements will be compared using the Student's t-test. As above, bivariate methods will also be used to assess any demographic or clinical characteristics that may be associated with acceptability. We will calculate treatment recovery time [63] as assessed by the extent to which participants missed school or work due to treatment recovery, required the help of others in their recovery, and the duration of physical and self-reported psychological symptoms as recorded on the daily diary maintained by participants.

In order to assess the impact of our results on health care costs, we will calculate whether there is an increased or decreased cost from adding mifepristone to the medical management regimen. Mifepristone is priced at \$90 per tablet. However, depending on how much it decreases extra medical and surgical care, this price may be more than off-set [64]. The cost for each woman will be computed including hospital resource costs (ER visits, physician time, ultrasounds, etc), cost to the woman (days off work, childcare expenses, travel expenses, etc), and lost productivity. Total costs will be compared between treatment arms using standard bivariate techniques. The nonparametric bootstrap method will be used to present cost-effectiveness acceptability curves and net benefit statistics at alternative willingness to pay thresholds held by decision makers for preventing a need for surgery [65].

Once all participant phlebotomy specimens have been obtained, we will be able to derive a predictive model for successful medical management vs. failure for all subjects. Separate predictive models will then be built for each treatment arm, and any differences found here will lay foundations for future research. Accurate assessment of gestational age (GA) can be a challenge in women who present with EPF, and GA may in fact be a confounder in the relationship between hormone levels and the nature of the demise. Depending on time of presentation relative to time of demise, biomarker levels may be more a reflection of the actual GA, or may in fact be impacted by duration of demise (i.e. β hCG, P_4 may start declining after demise occurs). We can utilize last menstrual period dating (LMP) with the caveat that LMP is not always certain. To overcome this measurement error problem, we will also analyze a

subset of women with a sure LMP and for whom ultrasound dating is consistent with LMP. If the model for this subset is consistent with the model for the full data, or GA is not found to significantly modify the relationship, only the full data model will be presented.

Biomarker levels will be summarized overall, and by treatment group, using standard descriptive statistics. We will use graphical methods, such as lowess smoothers, to determine the shape (linear or non-linear, potential cut-points for classifying levels) of the relationship between the biomarker level and probability of success, and subsequently for inclusion as predictors in a multivariable logistic model. We will analyze a subset of women with a sure LMP and for whom ultrasound dating is consistent with LMP separately for the most accurate analysis of the relationship between biomarker concentration and the characterization of an EPF that will respond well to medical management. We can compare this definitive LMP group to the group of women in whom LMP is unsure. We will calculate the sensitivity, specificity, and positive and negative predictive values for each biomarker. The predictive accuracy of different cutoffs will be evaluated using ROC curves.

Logistic regression and classification and regression trees (CART) will be used to develop a predictive model for successful management of early pregnancy failure, which will serve as the basis for a clinical predictive index [66-68]. Our group has used this methodology with success [69,70]. Initially the predictive model will only include biomarkers, and then both biomarkers and epidemiologic and clinical characteristics will be considered in the predictive model. The sensitivity of the predictive index (i.e., proportion of patients with success who are defined as “high chance of success” by the rule) will be of primary interest [71]. The negative predictive value will also be calculated using the derived sensitivity and specificity with the population prevalence of success. This value is also of clinical interest.

For model building, we will enter all biomarkers that will have shown in the bivariate analysis at least borderline associations with the endpoints of interest ($p < 0.20$), as well as interaction terms that are suggested by the results of the explanatory model. Terms will then be removed from the model using a backward elimination procedure, removing factors which cause an insignificant change in the sensitivity of the model. To test the change in sensitivity between models (with and without the variables), we will use McNemar’s test. In particular, we will be comparing the proportion of correctly classified cases of success between models. The rule would involve calculating a score for each person, based on the actual values of the regression coefficients. The goal is to utilize all variables that improve the sensitivity of the model. Unlike the explanatory model, whose goal is to determine which variables are associated with success, the predictive models will be developed in order to determine which combination of variables best predicts the outcome. Additionally, variables and interactions included in the model must be biologically plausible.

To be useful, a clinical rule must be easily applied. In order to ensure easy understanding and unhindered application, the variables and parameters comprising the predictive score will be simplified with two methods: 1) by recalculating the predictive score using values of the coefficients, rounded to the nearest integer, and 2) by calculating the score simply as the sum of the dichotomous independent variables identified by the model. (It will be necessary, for this approach to recode continuous predictors as dichotomous variables.) This will result in the most parsimonious model. The performance of the new rules will then be compared with that of more complete models using ROC curves. We plan to evaluate potential cutoffs of each marker to optimize our ability to distinguish among successes and failures.

We will also approach our predictive modeling using CART. Candidates that have an individual area under the curve (AUC) > 0.6 will be considered. CART is useful in identifying complex relationships between biomarkers and clinical outcomes. These analyses recursively split observations into two

groups (nodes), t_L and t_R , based on the covariate that maximizes a given split function. In the case of a continuous outcome, a commonly used split function is the reduction in sums of squares error, i.e. the amount of variability explained by the split. The best split is defined to be the one that best predicts the response where the best predictor is defined to be the one that maximizes the split function. All splits of the observations in each of the resulting nodes are then considered and the best split identified. This process is repeated recursively until a stopping rule is achieved (e.g. no further splits exist with greater than 5 observations in each of the resulting nodes). We will employ 10-fold cross-validation to assess the significance of the resulting tree as described in Breiman [72]. The sensitivity and specificity of the CART versus logistic model will be compared using ROC curves, to determine the best predictive rule for management success. CART software will be used to evaluate combinations of biomarkers creating a tree maximizing sensitivity and a tree maximizing specificity. Data will be combined into a three-tiered algorithm to maximize accuracy.

The prediction rule will be internally validated with a “bootstrap” approach [73-78]. With this approach, a large number of samples are taken from the original data (with replacement) and the predictive accuracy is tested in each of these samples. Sampling with replacement generates a population identical in composition to the observed sample. This method provides a relatively unbiased estimate of the test characteristics of the predictive rule [78].

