Statistical Methodology	
The study population will be summarized overall, and by treatment group, using standard descriptive statistics. Both intent to treat and compliant populations will be analyzed. For categorical data, chi-square test will be used. For continuous variables, t-test will be used if the distribution is normal; otherwise rank-sum test or log transformation will be used. The following outcomes will be evaluated:
 
 • Success rates between study arms for early pregnancy failure; • Side effect frequency, participant satisfaction, and acceptability of the treatment regimens; • Cost analysis to compare these two treatments. 
Logistic regression and classification and regression trees (CART) will be used to develop a predictive model for successful management of EPF that includes the biomarker analyses to be performed, which will serve as the basis for a clinical predictive index.

1 Introduction

This document is a protocol for a human research study. This study is to be conducted according to US and international standards of Good Clinical Practice (FDA Title 21 part 312 and International Conference on Harmonization guidelines), applicable government regulations and Institutional research policies and procedures.

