5.3. Method for Assigning Subjects to Treatment Groups

The subject will be randomly assigned to one of two study groups: 800 µg vaginal misoprostol (group 1) or 800 µg vaginal misoprostol preceded by 200 mg mifepristone orally (group 2). Randomization will be performed through a central randomization process using REDCAP. Participants will be randomized in a 1:1 ratio of treatment groups. Randomization will be stratified by research center.

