7.1. Sample Size Determination

Sample size calculations are based on detecting differences in the success rates between the misoprostol only and combined groups. Based upon prior research, we would expect a 60-71% single-dose success rate in the misoprostol only group [25]. Our preliminary data showed a 90% single-dose

success rate in the combined group using the proposed study regimen [11]. If we assume a conservative 85% success rate estimate for combined (C) and 70% success in the misoprostol only (M), we require 134 participants/group to show a difference if one is there (Table 2). To arrive at the total number of women needed to enroll, we inflate this estimate by 10% for loss to follow-up (5%) and interim analysis (5%). We will have adequate power to show a difference in success rates for all proportions above 10%. Thus, our proposed recruitment goal of 300 women (150/group) will enable us to find a clinically meaningful difference of 15% and confidently find the expected difference (20%) between groups.

Combination success rate	Misoprostol only success rate				
	50%	60%	65%	70%	75%
80%	n = 45 C: ±11.7% M: ±14.6%	n = 91 C: ±8.2% M: ±10.1%	n=151 C: ±6.4% M: ±7.6%	n = 313 C: ±4.4% M: ±5.1%	n = 1134 C: ±2.2% M: ±1.7%
85%	n = 33 C: ±12.2% M: ±17.1%	n = 57 C: ±9.3% M: ±12.7%	n=83 C: ±7.7% M: ±10.3%	n = 134 C: ±6.8% M: ±7.8%	n = 270 C: ±4.2% M: ±5.1%
90%	n = 25 C: ±11.8% M: ±19.6%	n = 38 C: ±9.5% M: ±15.6%	n=51 C: ±8.2% M: 13.1%	n = 72 C: ±6.9% M: ±10.6%	n = 113 C: ±5.5% M: ±8.0%
95%	n = 18 C: ±10.3% M: ±23.8%	n = 26 C: ±8.4% M: ±19.2%	n = 31 C: ±7.7% M: ±17.0%	n = 42 C: ±6.5% M: ±14.0%	n = 55 C: ±5.8% M: ±11.5%

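### Randomisation is stratified by center, but section 7.2 does not carry center consistently into the primary comparison, and no sentence names the final test that is held against the final alpha.

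*Combined protocol and SAP*

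**What the plan says.** On design, section 5.3 states: "Randomization will be stratified by research center". Section 10 (Monitoring Activities) describes enrolment at two sites.

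On site in the analysis, section 7.2 gives two instructions.
- Under Primary Analysis: "if there is no significant overall difference among the sites (homogeneous), we will pool sites together". If the sites do differ significantly, pairwise site comparisons with a Scheffe adjustment follow, and then "In all following analyses, site will then be an independent variable for adjustment". No significance level is given for the site test.
- Further on, for the logistic regression: "The final regression models will include the treatment group, study sites", together with characteristics associated with success at p<0.1 and "covariates that altered the unadjusted ratios by at least 10" per cent. Site carries no condition here.

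On the treatment comparison, the plan mentions several analyses.
- Study Summary and section 7.2: "For categorical data, chi-square test will be used". This has no site term.
- Section 7.2: relative risk and odds ratio, then logistic regression, then the multivariable model above. If baseline imbalance appears, one of three adjustment methods is to be used.
- Section 7.4: for the interim look, a simple logistic model with treatment as the only term. Alpha is split as 0.003 and 0.047, described as incremental values.

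Section 7.3 makes all randomised women the analysis population.

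**The concern.** A factor used to stratify randomisation should normally appear in the primary analysis. If it is left out and the factor affects outcome, the test is somewhat conservative and some power is lost. Letting a significance test on the trial's own outcomes decide whether to include it adds a data-dependent step that serves no purpose, because center is known for every woman from randomisation.

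The second issue is pre-specification. The primary question of a phase 3 trial should be settled by one named result. Here the final 0.047 stands in section 7.4, which names a model only for the interim comparison, while section 7.2 lists several analyses of the same comparison without ranking them. If the choice is written down only after the data are seen, it cannot be shown to be independent of the result.

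**Working it through.** **1. The plan's own sample size.** Section 7.1 says "we require 134 participants/group to show a difference if one is there (Table 2") for 70% versus 85%. It states neither power nor sidedness; I assume 80% and two-sided 0.05. With p̄ = 0.775 and d = 0.15,

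n = [1.960·√(2·0.775·0.225) + 0.842·√(0.70·0.30 + 0.85·0.15)]² / 0.15² = 120.5, so 121.

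With the continuity correction, (n/4)·[1 + √(1 + 4/(n·d))]² = 133.5, so **134**. The figure reproduces as a two-proportion calculation with no site term. Inflation gives 268 × 1.10 = 295 or 268/0.90 = 298, both consistent with 300.

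**2. The site instructions side by side.**

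| Site test | Primary Analysis paragraph | Final regression models | Chi-square; interim model |
|---|---|---|---|
| Significant | site adjusted for from then on | site included | no site term specified |
| Not significant | sites pooled | site included | no site term specified |

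The two instructions agree in the first row. They can be read differently in the second.

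**3. Cost of a pooled test.** Assumptions: 150 per group, two equal sites, arms balanced within site, success rates D apart between sites in both arms, two-sided level 0.047 (critical value 1.986).

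*Type I error at 70% success.* The true variance relative to the pooled variance is r = 1 − (D/2)²/(0.70·0.30). The error is 2·P(Z > 1.986/√r).
- D = 0.10: r = 0.988, error **4.6%**.
- D = 0.20: r = 0.952, error **4.2%**.

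*Power at 70% versus 85%.* Power = Φ[(0.15 − 1.986·SE₀)/SE₁], where
- pooled SE₀ = √(2·0.775·0.225/150) = 0.04822;
- stratified SE₀ = √(2·[0.775·0.225 − (D/2)²]/150);
- SE₁ = √([0.21 + 0.1275 − 2(D/2)²]/150).

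| D | Stratified SE₀ | SE₁ | Pooled power | Stratified power | Loss |
|---|---|---|---|---|---|
| 0 | 0.04822 | 0.04743 | 87.4% | 87.4% | 0 |
| 0.10 | 0.04787 | 0.04708 | 87.5% | 87.8% | 0.3 points |
| 0.20 | 0.04682 | 0.04601 | 88.1% | 89.2% | 1.2 points |

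The losses are taken from unrounded values.

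A simulation of 200,000 trials per setting, with site differences from 0 to 20 points, agrees. At nominal 4.7%, type I error was 4.2–4.8% pooled, 4.6–4.8% Mantel-Haenszel and 4.6–4.8% under the pre-test rule (site test at an assumed 0.05). Pooled and stratified tests reached different conclusions in at most 0.4% of null trials and 1.2% of trials under the planned effect.

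**4. What 0.047 means.** The two looks are taken as bivariate normal with correlation √0.5 (interim at half the information) and 0.003 two-sided at the interim.
- If 0.047 is the nominal final level, overall error is **0.0480**.
- If 0.047 is the increment that brings the total to 0.05, the nominal final level is about **0.0490**.

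Section 7.4 uses the word incremental but does not give the nominal final level.

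**The case against.** The best defence is that the primary test can be inferred. The chi-square test stands under the Primary Analysis label, the interim model contains treatment only, and the sample size compares two proportions. With one binary treatment, the chi-square and simple logistic tests are asymptotically equivalent. The prediction-model text in section 7.2 ("Unlike the explanatory model, whose goal is to determine which variables are associated with success") suggests that the covariate-selected model was not meant as the confirmatory test. Pooling could also refer to the simple tests alone, which would remove the difference in step 2.

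Most of this stands. The plan does lean to an unadjusted comparison, and it would be too strong to call the two site instructions irreconcilable. But the text does not state the reconciling reading, and the inferred test still omits the factor on which randomisation was stratified.

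A reader might go further and infer that type I error is inflated, because either the crude or the covariate-selected result could be claimed. Simulations with ten invented candidate covariates put overall error at 5.1–6.4% under that freedom, the lowest figure being within simulation error of 5%. The documents do not support this reading: no passage permits a choice between results. Taken singly, each route simulated stayed at 4.5–4.9%.

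A reader might also infer that the continuity correction behind 134 is a defect. It is not. By exact enumeration at 150 per group and level 0.047, power is 87.8% without and 84.6% with the correction, and type I error is 4.7% and 3.5%. Both powers exceed the assumed 80%. Which version to use is a detail to state.

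**Conclusion.** The point holds as a modest pre-specification and consistency gap that should be closed. The stratification factor is not carried consistently into the primary comparison, its use is partly tied to an outcome pre-test, and the final test is not named.

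The size is small: type I error slightly below nominal, and a power loss of about 0.3 to 1.2 points for site differences of 10 to 20 points. These figures assume two equal sites and balance within site; the documents give no site-specific success rates. The site pre-test does almost no measurable harm; the reason to drop it is that it is unnecessary. The planned sample size is not threatened.

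**What to change.** In section 7.2:
- Remove the site pre-test and the Scheffe step. With two sites there is only one pair, so the pairwise step adds nothing.
- Name one primary test in all randomised women, used at both interim and final: either a Mantel-Haenszel test stratified by center, or logistic regression with treatment and center. Either closes the gap. State whether a continuity correction applies.
- Label the models selected on p<0.1 or a 10% change, and those triggered by baseline imbalance, as supportive or exploratory.

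In section 7.4:
- Replace the interim model with the same test, and state that this result alone is compared with the interim and final thresholds.
- Say whether 0.047 is the nominal final level (overall error about 0.048) or incremental alpha (nominal level about 0.049).

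The cost is wording and a little analysis work. Center is known from randomisation, Mantel-Haenszel analysis is already mentioned in section 7.2, and N stays at 300. The change should be made before outcomes are compared by arm.

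### Name the mean cost difference, with a bootstrap interval, as the total-cost comparison: the general rule could send skewed costs to a rank-sum or log analysis that does not answer the $90 question

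*Combined protocol and SAP*

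**What the plan says.** All of the relevant text is in section 7.2 (Statistical Methods) of the combined protocol and SAP.

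- **General rule for continuous outcomes:** "For continuous variables, t-test will be used if the distribution is normal; otherwise rank-sum test or log transformation will be used". No normality test or criterion is named.
- **Cost is on the list of outcomes that follows the rule:** "Cost analysis to compare these two treatments".
- **Cost question:** "we will calculate whether there is an increased or decreased cost from adding mifepristone to the medical management regimen". The tablet is priced at $90, and the text adds that "depending on how much it decreases extra medical and surgical care, this price may be more than off-set".
- **Total-cost method:** "Total costs will be compared between treatment arms using standard bivariate techniques". Earlier in the section, t-tests and Mann-Whitney tests are the examples of bivariate methods for continuous or ordinal variables, in the context of comparing participant characteristics.
- **Bootstrap:** "The nonparametric bootstrap method will be used to present cost-effectiveness acceptability curves and net benefit statistics", to be shown "at alternative willingness to pay thresholds held by decision makers for preventing a need for surgery". The thresholds are not listed.

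Nothing exempts cost from the general rule, and no confidence interval for the mean cost difference is specified.

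**The concern.** Whether $90 is recovered is a question about arithmetic means. Every woman in the combined arm adds $90, while any saving comes from the minority whose failure is avoided, and only the mean balances the two. A rank-sum test asks whether a woman in one arm tends to cost more than a woman in the other. A comparison of log costs targets the ratio of geometric means. Most women in both arms are expected to succeed, so the typical combined-arm woman can cost more while the average falls.

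At stake is a real mean saving missed by the total-cost test, or a total-cost test and a net-benefit analysis that point in different directions, with no prior statement of which one answers the question.

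**Working it through.** **Plan's own figure.** The documents state no cost difference, cost SD or power for cost. The success rates behind any off-set are those of the sample size in section 7.1: 85% combined, 70% misoprostol only, 134 per group. Section 7.1 gives neither power nor sidedness; assuming 80% and two-sided 0.05:

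n = [1.96·√(2 × 0.775 × 0.225) + 0.84·√(0.85 × 0.15 + 0.70 × 0.30)]² / 0.15² ≈ 120.5, and with continuity correction ≈ 133.5, so 134. This matches.

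**Break-even.** With S the extra cost of a failure and Δ the difference in success rates, the mean cost difference (combined minus misoprostol only) is 90 − Δ·S, so break-even is S = 90/Δ.

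| Success rates | Δ | Break-even S |
|---|---|---|
| 70% vs 85% (sample-size case) | 0.15 | 90/0.15 = $600 |
| the 20-point difference section 7.1 calls expected | 0.20 | 90/0.20 = $450 |
| 60% vs 90% (low end of the control range, pilot rate) | 0.30 | 90/0.30 = $300 |

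**Rank and log can differ in sign from the mean.** Assume a lognormal base cost of about $300 (log-SD 0.3), S = $1,000 and Δ = 0.15. The mean difference is 90 − 150 = −$60, a saving. Yet the probability that a combined-arm woman costs more than a control woman is 0.59, and the geometric mean ratio is 1.04. Both point to the combination as dearer.

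**How often it would matter.** The only unit cost in the documents is $90, so everything else here is assumed. Set-up: 150 per arm, failures 15% vs 30%, gamma-distributed other costs, $90 added for each combined-arm woman, S added for each failure, two-sided 0.05, 2,000 to 5,000 simulated trials per setting. Entries are the percentage of trials with a significant saving.

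| Other costs | S | True mean saving | Means | Rank-sum |
|---|---|---|---|---|
| mean $600, SD $300–600 | $800 | 120 − 90 = $30 | 6–8% | 3.5–4.4% |
| mean $600, SD $300–600 | $1,500 | 225 − 90 = $135 | 27–40% | 7–12% |
| mean $600, SD $300–600 | $2,500 | 375 − 90 = $285 | 54–65% | 5–14% |
| mean $1,500, SD $750–1,000 | $1,500 | $135 | 17–21% | 17–19% |

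In the $600-mean model the log comparison finds the saving in about 1–10% of trials at $1,500 and 2–23% at $2,500.

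Two variations show how far the result moves:

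- **Larger treatment effect.** At 65% vs 85% success, with other costs of mean $600 and S = $1,500, means detect the saving in 57–74% and rank-sum in 26–31%.
- **Cost floor.** If every woman incurs at least $300 within the same $600 mean (SD $300–600, S = $1,500–2,500), the rank-sum result is significant in the wrong direction in 3–37% of trials. Without the floor the figure is 0.2–1.8%.

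**Does the proposed analysis behave?** A percentile bootstrap 95% interval for the mean difference (1,000 resamples, 800 trials per setting) covered the true value in 93.5–95.6% of trials in the $600-mean model.

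**The case against.** Four arguments deserve weight.

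1. **The plan does not say that costs will be ranked or logged.** A reader might infer that rank-sum or log is the planned cost analysis. The text does not go that far. Standard bivariate techniques can include a t-test, no normality criterion is named, and the t-test/Mann-Whitney examples are tied to participant characteristics. Section 7.2 also compares VAS scores by Student's t-test without a normality condition, so outcome-specific text can depart from the general rule. This stands, and the claim is limited to what could follow. The VAS sentence also shows that the authors name a method where they want one, and for cost they did not.

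2. **A mean-based analysis is already planned.** A reader might infer that the plan lacks one, and that would be wrong. Net benefit rests on mean costs, and at a willingness to pay of zero it equals minus the mean cost difference. But the documents do not say that zero is among the thresholds, specify no interval for the mean difference, and assign total costs to a separate technique. What remains is a matter of naming and precedence.

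3. **The loss rests on assumed costs.** This stands. The planned costing includes days off work, childcare, travel and lost productivity, so other costs could well average more than $600, and at $1,500 with a $1,500 failure cost the methods nearly agree. A cost floor pushes the other way. A reader might also infer that a rank-sum test would generally declare the combination dearer; that occurs in some assumed cost structures and is at chance level in others.

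4. **Cost is one of several secondary endpoints.** This also stands, and it limits the severity.

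**Conclusion.** The point holds as a minor clarification. Read naturally, the plan could compare skewed total costs by a method that does not estimate the mean difference, although its own cost question is about the mean. The quantity it needs is already implicit in the planned bootstrap but is not named as the total-cost result, so two cost results could disagree with no stated precedence.

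The break-even figures ($600, $450 and $300 per failure avoided) follow from the plan's own numbers. Skewness is inferred from the expected 15–30% failures; it is not stated in the documents. The detection rates rest on assumed cost distributions and run from a large gap to almost none. They are illustrations, not bounds. The primary analysis, sample size and primary conclusion are unaffected.

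**What to change.** In the cost paragraph of section 7.2, replace the reference to standard bivariate techniques with one sentence: total costs will be compared by the difference in arithmetic mean cost per woman between arms, with a nonparametric bootstrap 95% confidence interval from the same resampling used for the net-benefit analysis. Add that cost is exempt from the rank-sum/log rule and that any rank or log result is supportive at most.

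This is a free improvement: one sentence of SAP wording and a short exemption, with no additional data, participants or visits. It should be made before cost data are compared by arm, so that the choice of method cannot depend on the result.
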